Coordinating Clinical Investigator	[name] Chief Physician Ass. Professor, PhD, specialist in dermatology DK MD registration ID: [name] Department of dermatology, Bispebjerg University Hospital [name] Email: [contact]
Principal investigator Denmark	[name] Chief Physician Professor, dr. med., specialist in dermatology DK MD registration ID: [name] Department of dermatology, Bispebjerg University Hospital, [name] Email: [contact] [contact]
Principal investigator Sweden	[name] [name], PhD, specialist in dermatology SE MD registration ID: [name] Department of Dermatology and Venereology, Sahlgrenska University Hospital [name] Email: [contact] [contact]
Investigator Sweden	[name] Chief Physician PhD, Specialist in Dermatology Department of Dermatology and Venereology, Sahlgrenska University Hospital [name]
GCP support Denmark (pending contract)	GCP-enheden ved Københavns Universitetshospital Frederiksberg Hospital [name] E-mail:[contact] Tlf: [name]
GCP support Sweden (pending contract)	Gothia Forum for Clinical Studies Research Support Office Sahlgrenska University Hospital [name] Email: [contact] [contact]

Table 1. Planned activities in the clinical investigation. The investigation consists of a single treatment session (Visit 2) with 3 subsequent follow-up evaluations. The first data analysis and report on primary end-points will be done as an interim assessment after the 3-month visit has been completed by all participants (Visit 4). Primary and secondary end-points are concluded in a final report after all participants have completed the 9-month visit (Visit 5).

Visit number	1	2	3	4	5	6
Event Name	Pre-study	Day 0	7 ± 3 days	12 ± 2 weeks	24 ± 2 weeks	39 ± 3 weeks
			(1 week)	(3 months)	(6 months)	(9 months)
	Consent, Screening and Enrollment	Pre-treatment documentation, treatment, and post- treatment assessments	Evaluation of wound generation	Evaluation of healing and surveillance for any new lesions	Evaluation of healing and surveillance for any new lesions	Evaluation of healing and surveillance for any new lesions
Clinical evaluation	х	x	х	х	х	x
Inclusion and registration	х					
Informed consent	х					
Photo documentation 2D		X1	х	х	х	x

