The investigational device is a Danish developed system aimed specifically at high frequency operation (20 MHz). At this high frequency, the device, as the first of its kind, allows controlled and targeted treatment of small intradermal volumes, thus with limited damage to the surrounding tissue.

The investigational device has passed pre-clinical studies in experimental laboratory models and in a safety study on Göttingen minipigs as reported in the IB and published in the literature (23, 24).

The pre-clinical experiments showed the following key results and conclusions:

- The 20 MHz ultrasound output is a well-defined ultrasound cone with a sharp focal point as demonstrated in laboratory measurements and in tissue-mimicking phantom gel simulating skin.
- The produced thermal lesion is highly reproducible from dose to dose.
- The depth of the focal point can be chosen and positioned as intended depending on the selected hand piece.
- The temperature in the focal point reproducibly matches 65 °C.

- The extension/severity of the heat effect in a phantom and read as necrotizing effect and heat lesion in the pig study was tunable within the range of available instrument settings, and reproducible.
- Depending on device setting, non-ablation subclinical effects can be induced, alternatively ablation/necrotizing effects, the former being relevant for cNF therapy.
- Post-treatment wound and healing studied in the pig followed over time (12 weeks) depended on the applied ultrasound energy.
- Isolated single dosing had much lower, or no, necrotizing effects as compared to multiple shoulder-by-shoulder dosing applied to a larger field.
- Histology after three months indicated mild fibrosis in pigs treated with higher ultrasound energy, however, clinical scar formation was not visible, or only barely visible.
- Studies indicated the depth of the ultrasound lesion in the dermis are well controlled by way of proper selection of instrument settings, and the choice of hand piece.
- Depending on dose, a transient wheal and flare reaction, with redness and edematous swelling, occurred within minutes and faded within about 30 min. This reaction is comparable to skin reactions from dermatological lasers. The reaction is considered to be caused by traumatic histamine release.
- Ultrasound treatment in clinical use may be associated with instant pain and possibly itch.
- Studies indicated no unexpected adverse events, and no systemic safety concerns.

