5.1 Primary endpoint - Tolerability

- The grade of any adverse events (AE) requiring medical intervention within three months of treatment should be low. Device-based treatment will be considered tolerable if less than 30% of participants treated have an "Overall AE Score" larger than Grade 2 AE at the 3month follow-up (visit 4) as assessed via Common Terminology Criteria for Adverse Events (CTCAE), U.S. Department of health and human services, Ver 5.0, Nov 27, 2017.
- The rate and nature of spontaneous healing of the treated cNF lesion and any safety related event including potential wound formation and wound healing should be equivalent to expectations from alternative method(s). Safety evaluation includes rating of treatment associated sequele by end of study, e.g. dyspigmentation and scarring and overall investigator rating compared to expectations.

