5.2 Secondary endpoints – Efficacy, safety and feasibility

- Efficacy: Rate of clearance, e.g. reduction of tumor mass of treated cNFs based on 2D and 3D photography or ultrasound imaging assessment at 3 and 9 months parallel to assessment of the degree of dyspigmentation with hypermelanosis or hypomelanosis of the lesion and the perilesional untreated skin.
- Safety: Itch and pain from the treatment measured on a 0-10 point numerical scale.
- Safety: Wheal and flare reaction and inflammatory responses are measured on a graded scale.
- Safety: Any objective adverse effect or event, local or systemic, related to the treatment and the investigational device is measured (wound and course of wound healing, scar formation, instrumental hazards) is categorized immediately after treatment and at all follow-up visits.
- Feasibility: Feasibility is evaluated both quantitatively (time spent on treatment) and qualitatively depending on the object considered and cover elements that may compromise or favor HIFU relative to other treatments employed for lesions in clinical practice or from the literature. Feasibility assessment will not produce a direct comparison with alternative methods since the study has no arm with an alternative method. The evaluation comprise the following essentials:
 - 1) Time and resource spent on the treatment session using the device,
 - 2) Investigators' assessment of the practice of using the device and the treatment,
 - 3) Participants" assessment of satisfaction with the treatment and the device.

All skin toxicities will be grated according to the classifications in Common Terminology Criteria for Adverse Events (CTCAE), U.S. Department of health and human services, Ver 5.0, Nov 27, 2017.

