Clinical recording of the study includes clinical assessment of healing and therapeutic effect on the tumors. Such assessment follows clinical criteria described in textbooks, guidelines and clinical consensus in the specialty of dermatology. Prior to study, the two investigator sites have coordinated their clinical assessment method.

The chosen 9-month total study period is considered acceptable for observation of tolerance and curative effect of HIFU for cNF with observation of primary therapeutic effect after 3 months. Assessments includes monitoring of the wound healing phase, observation of late recurrences, and observation of scarring.

The study includes no follow up medication, but the study can involve use of wound healing dressings and other remedies in the wound healing phase on investigators individual recommendation. The study involves no standard recommendation on post treatment care, which is anticipated to be simple.

After the study participants are followed in the respective hospital departments according to their needs and the department routines.

Participants who drop out of the study before the 3-month visit voluntarily or for non-medical reasons, including non-adherence, will be replaced by new participant(s). Withdrawals after 3 months are replaced on investigators discretion with considerations to the impact of the overall investigation schedule.

Patient with incomplete cure documented by ultrasound imaging assessment or biopsy and histology after 3 months or subsequent control visit (indicated by clinical suspicion of reoccurrence) will be offered a second treatment based on the standard treatment offered by the center. The specific treatment will be decided by the investigator and the patient based on the extent and severity of the recurrence.

The study will conclude when all participants have completed the 9-month study period, when all data are on file, and the statistical analysis is concluded. Interim analysis of data collected after 3 months and later is allowed, per investigator's decision.

If the study design is deemed inferior, the protocol can be amended.

The study produces no physical test samples relevant for purposes outside the study.

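### Healing rate is listed under the primary endpoint, but no assessment is scheduled between day 10 and day 70, so the visits cannot show how fast a wound healed

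*Combined protocol and SAP*

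**What the plan says.** Three places in the combined protocol and SAP commit the trial to assessing healing.

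- Section 5.1, second bullet under the primary endpoint: "The rate and nature of spontaneous healing of the treated cNF lesion", together with any wound that forms and its healing, is to match what would be expected of alternative methods. *Rate* is given no unit, time point or threshold.
- Section 5.2, among the secondary safety items: "wound and course of wound healing, scar formation, instrumental hazards) is categorized immediately after treatment and at all follow-up visits".
- Section 6.6: "Assessments includes monitoring of the wound healing phase".

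Table 1 fixes the observation times. Visit 3, at 7 ± 3 days, has the stated purpose "Evaluation of wound generation". The next visit is at 12 ± 2 weeks, followed by 24 ± 2 and 39 ± 3 weeks. The caption of Table 1 says "The investigation consists of a single treatment session (Visit 2) with 3 subsequent follow-up evaluations" while the table shows four follow-up visits, but neither count puts a visit between week 1 and week 12. Section 6.3.1 repeats the same times for ultrasound, Section 6.6 lists no photograph between 1 week and 3 months, and Section 7 ties the adverse-effect grade to the same visits. No telephone contact, diary or closure date is described.

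**The concern.** Read as speed, the rate of healing needs a closure time that is known reasonably well. The same holds for the course of healing. Under this schedule, a wound seen at visit 3 and gone at visit 4 has a closure time known only to lie in an interval of two to three months. A two-week and a ten-week closure would be recorded alike, and neither could be compared with the healing expected of another method.

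The protocol does not treat slow healing as negligible. Section 14.4 names delayed wound healing as a possible result of a stronger burn than anticipated, and Section 4 lists wound-healing complications among the anticipated local effects. In a first systematic study of 20 participants, each wound that does occur is informative.

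**Working it through.** **The plan's own figure.** The plan gives no number for healing. Its sample size concerns the adverse-event grade only: N = Z² × P × (1 − P) / e² = 1.96² × 0.90 × 0.10 / 0.15² = 15.37, rounded up to 16, with 20 planned. This reproduces, and healing time does not enter it.

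**Inputs (Table 1).** Visit 3 is at day 7 ± 3, so days 4 to 10. Visit 4 is at week 12 ± 2, so day 84 ± 14, or days 70 to 98.

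**Gap.** Gap = day of visit 4 − day of visit 3. A wound that closes on day c is recorded as open at visit 3 and closed at visit 4 when (day of visit 3) < c ≤ (day of visit 4).

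| Timing | Visit 3 | Visit 4 | Gap (days) | Closure days giving open, then closed |
|---|---|---|---|---|
| Nominal | 7 | 84 | 84 − 7 = 77 | 8 to 84 |
| Shortest gap | 10 | 70 | 70 − 10 = 60 | 11 to 70 |
| Longest gap | 4 | 98 | 98 − 4 = 94 | 5 to 98 |

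**What always holds.** The days common to every permitted pair of visit dates are 11 to 70. Closure on any of them gives the same record at visits 3, 4, 5 and 6, whatever in-window dates are used. That spans 11/7 = 1.6 weeks to 70/7 = 10 weeks. Day 70 is the limit: if visit 4 falls on day 70, closure on day 71 is recorded differently.

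**Wounds that open late.** A wound that opens after visit 3 and closes before visit 4 is absent at both visits and leaves no trace in the visit findings.

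**Sites lost to biopsy.** Table 1 requires at least one treated lesion to be biopsied at visit 3 in each Swedish participant. With 10 Swedish participants, at least 10 × 1 = 10 treated sites leave clinical follow-up then (Section 6.3.2), so their healing cannot be followed to visit 4 under any scheme.

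**The case against.** **Rate may not mean speed.** Section 5.1 does not define it, and Section 5.2 uses the word for extent when it speaks of clearance. Read as the proportion healed, it is measurable on this schedule. This stands, which is why a wording change alone is an adequate fallback. It does not settle what Section 5.2 means by course.

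**Open wounds are not expected.** The hypothesis in Section 5 is healing without open wounds. Healing of the treated volume itself is followed by ultrasound in Denmark and by biopsy in Sweden. This stands as a limit on how many participants are affected. But the absence of wounds is what the trial sets out to test. Section 2.1 also leaves the investigator free to choose any available hand piece and says that this choice can make treatment ablative, and Section 6.6 provides for dressings during wound healing.

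**Adverse-event records could supply the dates.** Section 14.4 asks for date and resolution, and visit 4 includes event reporting and questions to participants. A reader might infer that delayed healing goes undetected unless it outlasts visit 4; given these records, that is too absolute. The mitigation is still partial: it needs the wound to be logged as an event, and the date then comes from recall or unscheduled contact. The CRF is not among the documents, so a closure-date field cannot be ruled out. The plan simply does not describe one.

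**The pig study.** Section 3 reports "Post-treatment wound and healing studied in the pig followed over time (12 weeks) depended on the applied ultrasound energy". A reader might infer that the unobserved weeks are the informative ones. The sentence does not say when wounds closed or when energy groups diverged, so it cannot carry that conclusion.

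**Conclusion.** The point holds in a limited form. If a wound forms, its closure time cannot be resolved within days 11 to 70 from the scheduled visits, so speed and course of healing cannot be reliably estimated from them. The unobserved interval is 60 to 94 days, nominally 77. This assumes visits within their windows and no interim contact beyond what the plan describes.

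A reader might infer that the primary endpoint fails, or that healing cannot be assessed at all. The documents support neither. Section 7 makes the adverse-effect grade the main measurable endpoint. The 30% criterion, the sample size and the power all rest on that grade and are unchanged. Whether a site is healed at week 1 and at month 3 is observable.

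The number of wounds cannot be predicted from the documents and may be small. This is a cheap improvement worth making, not a fault in the tolerability decision.

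**What to change.** Give every participant a dated card at visit 2 or 3 on which to record the opening and closure of any wound at each treated site. It should go to all participants, not only those with a wound at visit 3, so that later wounds are caught. Biopsied sites drop out from the time of biopsy. Collect the card at visit 4 and add one CRF field for the dates. Summarise time to closure descriptively as interval-censored data; with few wounds expected, no formal test is warranted. A weekly entry would narrow the interval from 60 to 94 days to 7.

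The cost is a one-page card and one CRF field, with no extra visit. The downside is minor participant burden and self-reported dates.

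If the card is not adopted, define *rate* and *course* in Sections 5.1 and 5.2 as the proportion of treated sites healed at visit 3 and at visit 4, with sites biopsied at visit 3 left out of the visit 4 denominator, and make no claim about healing speed. That costs only the rewording.

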5.2 Secondary endpoints – Efficacy, safety and feasibility

- Efficacy: Rate of clearance, e.g. reduction of tumor mass of treated cNFs based on 2D and 3D photography or ultrasound imaging assessment at 3 and 9 months parallel to assessment of the degree of dyspigmentation with hypermelanosis or hypomelanosis of the lesion and the perilesional untreated skin.
- Safety: Itch and pain from the treatment measured on a 0-10 point numerical scale.
- Safety: Wheal and flare reaction and inflammatory responses are measured on a graded scale.
- Safety: Any objective adverse effect or event, local or systemic, related to the treatment and the investigational device is measured (wound and course of wound healing, scar formation, instrumental hazards) is categorized immediately after treatment and at all follow-up visits.
- Feasibility: Feasibility is evaluated both quantitatively (time spent on treatment) and qualitatively depending on the object considered and cover elements that may compromise or favor HIFU relative to other treatments employed for lesions in clinical practice or from the literature. Feasibility assessment will not produce a direct comparison with alternative methods since the study has no arm with an alternative method. The evaluation comprise the following essentials:
 - 1) Time and resource spent on the treatment session using the device,
 - 2) Investigators' assessment of the practice of using the device and the treatment,
 - 3) Participants" assessment of satisfaction with the treatment and the device.

All skin toxicities will be grated according to the classifications in Common Terminology Criteria for Adverse Events (CTCAE), U.S. Department of health and human services, Ver 5.0, Nov 27, 2017.

5.3 Exploratory endpoints – Diagnosis and measurement methods

A core question to be addressed in this study is the effects of the thermal energy delivered to the treated cNF. Specifically, the study will seek to understand if the entire cNF tumor receives equal thermal energy by the method, if there are differences in dose relative to depth of the lesion, and what the inflammatory response within and around cNF is at one week (in the early stage of reaction) and after 3-6 months when coagulation and connective tissue repair are expected to be completed.

The inflammatory infiltrate observed after one week will indicate the severity and extension of the HIFU thermal effect on the cNF, and it can be assesses if the entire lesion was given full treatment or not. This data will be necessary to select recommended instrument setting and dose interval in future efficacy studies.

Both centers will assess the tumor's horizontal extension and skin elevation including typing (flat, sessile, globular) before and after treatment using 2D and 3D digital images as a part of the secondary efficacy endpoint. Additional exploratory end-point for qualitative and quantitative evaluations of the above characteristics and response to the method will be based on existing expertise and routine at the respective centers.

5.3.1 Ultrasound imaging assessment and characterization of treated CNF (Denmark)

Ultrasound imaging assessment will be used to assess the vertical thickness and depth of tumors at each time point of the study using a 20 MHz B-Mode ultrasound scanner. The scanner allows non-invasive measurement of tumor depth, cross-section area and quantitative characterization of e.g. various inflammatory responses. Measurements made on the tumors before HIFU, immediately after treatment, and at all follow-up visits will be noted directly in the study CRF. The combined conclusions regarding the use of ultrasound imaging assessment as a method for assessing the safety and efficacy of the HIFU treatment of cNF will be summarized by the center investigator in the final study report.

5.3.2 Biopsy of Cutaneous Neurofibroma (Sweden)

In Sweden, treated and reference untreated cNF from the same anatomical region will be subjected to biopsy and histological evaluation as a means of characterizing the above post-treatment characteristics. Small punch biopsies are preferred, but the investigator may decide to perform a surgical biopsy, or a shave biopsy, depending on participant's preference and the aim to possibly remove the entire lesion with the biopsy.

After the first three patients have been treated and have had the 3-month biopsy completed, the tissue will be assessed by histopathologists to assess if the pathology is stationary or not. The combined conclusions regarding the use of biopsy as a method for assessing the safety and efficacy of the HIFU treatment of cNF will be summarized by the center investigator in the final study report.

6 Design of the clinical investigation

6.1 General

The study is a two-center, open-label study in humans (hospital outpatients).

The two centers are both located in EU, and thus follow the same overall regulatory framework for clinical research and approvals.

The center located in Denmark, Department of Dermatology, Bispebjerg Hospital Region Copenhagen Capital, is a department under the Copenhagen University. The department provides advanced dermatological treatment, and is the largest dermatology department in Denmark.

The center located in Sweden, Sahlgrenska University Hospital is a non-profit University hospital owned and managed by Västra Götaland Region. It is a secondary referral center for dermatological patients and serves a population of about 750 000 in and around city of Gothenburg.

6.2 Selection and grouping of tumors

Tumors to be included in the study will be selected and documented in the treatment session (visit 2) via collaboration between the participant and the treating physician. According to the willingness of the participant there may be 1-3 triplets of tumors representing all three categories (flat, sessile and globular) which would make a total of 3-9 cNF tumors treated and 3-7 cNF tumors biopsied per participant. The minimum number of cNF to be treated is three. The maximum number of cNF to be treated is 9. The minimum number of cNF to be biopsied is 3 and the maximum number of cNF to be biopsied is 7 to limit discomfort or inconvenience associated with healing. Ideally, paired sets of tumors representing all three categories (flat, sessile and globular) will be included. However, it is acknowledged that this may not be feasible to identify all three categories of tumors in pairs in each participant. It will be noted in the CRF which cNF is the control/reference and which are treated and sampled. The selected tumors will be documented by 2D and 3D photos.

